6.3 Trial Endpoints

6.3.1 Primary Endpoint

Reduction in weekly PS volume from baseline to Week 24

6.3.2 Key Secondary Endpoints

- Clinical response, defined as achieving at least 20% reduction in weekly PS volume from baseline to both Weeks 20 and 24
- Reduction in days on PS ≥ 1 day/week from baseline to Week 24
- Reduction in weekly PS volume from baseline to Week 12

6.3.3 Reduction in weekly PS volume of 100% (weaned off) at Week 24Secondary Efficacy Endpoints

- Reduction of at least 20% in PS volume from baseline to both Weeks 12 and 24
- Change in fluid composite effect (FCE) from baseline to Week 24
- Reduction in calculated energy content of parenteral macronutrients from baseline to Week 24
- Reduction in number of days on PS per week from baseline to Week 24
- Reduction of at least 40% in PS volume from baseline to both Weeks 20 and 24
- PGIC improvement at Weeks 4, 12, 20, and 24

- Change in weight from baseline to Week 24

6.3.4 Other Efficacy Endpoints

- Reduction in days on PS \geq 2 days/week from baseline to Week 24
- Reduction in days on PS \geq 3 days/week from baseline to Week 24
- Reduction in duration of PS infusions per week from baseline
- Concentration trough levels of glepaglutide and metabolites
- Change in plasma citrulline level from baseline to Week 24
- Change in weekly need for parenteral micronutrients (sodium, potassium, magnesium, and calcium) from baseline to Week 24
- Change in patient-reported outcomes (SBS-I and EQ-5D-5L) from baseline to Week 24
- Reduction in bowel movements or stoma bag emptying from baseline to Week 24

6.3.5 Safety Endpoints

- Incidence and type of AEs and SAEs
- Changes in clinical evaluations:
 - Vital signs
 - Electrocardiogram (ECG)
- Changes in safety laboratory assessments:
 - Hematology
 - Biochemistry
 - Urinalysis
 - Standard bone markers
- Immunogenicity

6.4 End of Trial Definition

A patient will be considered as having completed the trial when:

- Patient completed EOT visit and exit interview, if consented (Danish, French, German, UK and US, sites only) and will continue participation in Extension Trial.
- Patient completed Follow-up (FU)/Final Visit and exit interview, if consented (Danish, French, German, UK, and US, sites only) and will not enter the Extension Trial.

6.5 Criteria for Premature Termination of the Trial and/or Trial Site

The Sponsor, the Institutional Review Boards (IRBs)/Independent Ethics Committees (IECs), or a Regulatory Authority may decide to stop the trial, part of the trial, or a trial site at any time.

The trial will be prematurely terminated overall or at a particular trial site at any time in the emergence of any safety information that could significantly affect continuation of the trial, i.e.

adverse events or other safety information that are considered unacceptable taken the indication into account and resulting in an unacceptable benefit-risk ratio. Guidance for when the Safety Committee will take action is provided in [Section 11.4.6](#).

If the trial is suspended or prematurely terminated, the Investigator must inform the patients promptly and ensure appropriate therapy and follow-up. The Investigator and/or Sponsor must also promptly inform the Regulatory Authorities and IRBs/IECs and provide a detailed written explanation.

If, after the termination of the trial, the benefit-risk analysis changes, the new evaluation must be provided to the IRBs/IECs in case it has an impact on the planned follow-up of patients who have participated in the trial. If it has an impact, the actions needed to inform and protect the patients should be described.

7 Trial Patients

7.1 Number of Patients

A total of approximately 108 patients are planned to be randomized into the trial; approximately 72 to the glepaglutide treatment groups (36 in each of the 2 active treatment groups) and approximately 36 to the placebo treatment group, after the PS Stabilization Phase is completed. A screen failure rate of 15% is expected, hence, approximately 152 patients may need to be screened.

7.2 Inclusion Criteria

The patient must meet all of the following inclusion criteria:

1. Informed consent obtained before any trial-related activity.
2. Age ≥ 18 years and ≤ 90 years at Screening.
3. Diagnosis of SBS defined as remaining small bowel in continuity of estimated less than 200 cm [equal to 79 inches] and with the latest intestinal resection being at least 6 months prior to Screening and considered stable with regard to PS need. No restorative surgery planned in the trial period.
4. Requiring PS at least 3 days per week.
5. Willing to adhere to an individual pre-defined drinking menu during 48-hours measuring intervals.
6. Willing to maintain a stable weight ($\pm 5\%$) for the duration of the trial (24 weeks).
7. Having:
 - a. A stoma Or
 - b. Colon-in-Continuity (CiC) with documented colonoscopy performed during Screening and which does not give rise to any safety concerns.
1. Note: A colonoscopy performed within 6 months prior to Screening and not giving rise to any safety concerns is accepted. For patients with a remnant colon, which is not connected to the passage of foods and is thereby dormant, a computerized

tomography (CT) scan or magnetic resonance imaging (MRI) (if standard of care at site) will suffice at the discretion of the investigator.

8. Having a) a stoma Or b) colon-in-continuity (CiC) and able to separate stool and urine during the 48 hours measuring intervals.

7.3 Exclusion Criteria

The patient must be excluded from the trial if he or she meets any of the following criteria:

1. More than 2 SBS-related or PS-related hospitalizations (e.g., catheter related bacteremia/sepsis, bowel obstruction, severe water-electrolytes disturbances, etc.) within 6 months prior to Screening.
2. Poorly controlled inflammatory bowel disease (IBD) that is moderately or severely active or fistula interfering with measurements or examinations required in the trial.
3. Bowel obstruction.
4. Known radiation enteritis or significant villous atrophy, e.g., due to active celiac disease.
5. Cardiac disease defined as: decompensated heart failure (New York Heart Association [NYHA] Class III-IV), unstable angina pectoris, and/or myocardial infarction within the last 6 months prior to Screening.
6. Clinically significant abnormal ECG as judged by the Investigator.
7. Repeated (2 or more consecutive measurements separated by at least 15 minutes) systolic blood pressure measurements > 180 mm Hg.
8. HIV (human immunodeficiency virus) positive, acute liver disease, or unstable chronic liver disease.
9. Any history of colon cancer. History of any other cancers (except margin-free resected cutaneous basal or squamous cell carcinoma or adequately treated *in situ* cervical cancer) unless disease-free state for at least 5 years.
10. Estimated creatinine clearance (CLcr; by the Cockcroft-Gault formula) < 30 mL/min.
11. Hepatic impairment defined as:
 - a. Total bilirubin $\geq 2 \times$ the upper limit of normal (ULN), or
 - b. Aspartate aminotransferase (AST) $\geq 5 \times$ ULN, or
 - c. Alanine aminotransferase (ALT) $\geq 5 \times$ ULN
12. Use of GLP-1, GLP-2, human growth hormone (HGH), somatostatin, or analogs thereof, within 3 months prior to Screening.
13. Use of dipeptidyl peptidase (DPP)-4 inhibitors within 3 months prior to Screening.
14. Systemic immunosuppressive therapy that has been introduced or has been unstable within 3 months prior to Screening.
15. Unstable biological therapy (e.g. anti-TNF- α , natalizumab, etc.) within 6 months prior to Screening, including significant changes in doses or switch of drug.

16. Females of childbearing potential, who are pregnant, breast-feeding, intend to become pregnant or are not using highly effective contraceptive methods. Highly effective contraception methods and definition of child-bearing potential are described in [Section 11.4.4](#).
17. Known or suspected hypersensitivity to glepaglutide or related products.
18. Previous exposure to glepaglutide.
19. Previous participation (randomization) in this trial.
20. Current, or within 30 days prior to Screening, participation in another interventional clinical trial that includes administration of an active compound.
21. Mental incapacity or language barriers which preclude adequate understanding or cooperation, or unwillingness to comply with trial requirements.
22. Any condition or disease or circumstance that in the Investigator's opinion would put the patient at any undue risk, prevent completion of the trial, or interfere with the analysis of the trial results.
23. Committed to an institution by virtue of an order issued either by the judicial or the administrative authorities.
24. An employee of the sponsor or Investigator or otherwise dependent on them.

7.4 Randomization Criteria

The patient must meet all of the following criteria at the time of randomization:

2. Requiring PS at least 3 days per week and maintains a stable PS volume for at least 2 weeks. PS volume is considered stable if all of the criteria below are fulfilled:
 - Actual PS usage (volume and content) matches prescribed PS ($\pm 10\%$ deviation in volume is acceptable) and
 - 48-hour urine volumes at 2 consecutive visits within a 2-week interval (± 4 days, i.e., visits should be 10 to 18 days apart) are similar (a maximum of $\pm 25\%$ deviation is acceptable), while the oral fluid intake is constant (the two 48-hour oral intakes differ less than 10%) and maximum 3.5 L per day and
 - Urine volume is on average ≥ 1 L per day and ≤ 2.5 L per day
3. No SBS-related hospitalizations within 30 days prior to randomization. Note: Hospitalizations related to trial procedures are allowed.
4. Since Screening, no poorly controlled IBD that is moderately or severely active or fistula interfering with measurements or examinations required in the trial.
5. No bowel obstruction since Screening.
6. No cardiac disease defined as: decompensated heart failure (New York Heart Association [NYHA] Class III-IV), unstable angina pectoris, and/or myocardial infarction since Screening.
7. No clinically significant abnormal ECG as judged by the Investigator.

8. Repeated (2 or more consecutive measurements separated by at least 15 minutes) systolic blood pressure measurements ≤ 180 mm Hg.
9. No use of GLP-1, GLP-2, human growth hormone (HGH), somatostatin, or analogs thereof since Screening.
10. No use of dipeptidyl peptidase (DPP)-4 inhibitors since Screening.
11. No systemic immunosuppressive therapy that has been introduced or has been unstable since Screening.
12. No unstable biological therapy (e.g. anti-TNF- α , natalizumab, etc.) since Screening, including significant changes in doses or switch of drug.
13. No unstable doses (including as needed use) within 2 weeks prior to randomization:
 - Antimotility drugs, e.g., loperamide, diphenoxylate, codeine or other opiates
 - H2 antagonists
 - Anti-diarrheal agents
 - Bile acid sequestering agents
 - Oral glutamine
 - Proton pump inhibitors
 - Diuretics
 - Systemic antibiotics or antibiotics affecting the gastrointestinal tract
 - Oral rehydration fluids
14. Females of childbearing potential, using highly effective contraceptive methods and who are not pregnant, breast-feeding, or intend to become pregnant.

7.5 Patient Withdrawal or Discontinuation from Trial Treatment

The patient is free to withdraw consent at any time during the trial. The patient's request to withdraw from the trial must always be respected.

All data collected from a withdrawn patient prior to withdrawal and during the final visit will be included in the analyses of the trial data. Although a patient is not obliged to give his/her reason(s) for withdrawing consent, the Investigator must make a reasonable effort to ascertain the reason(s), while fully respecting the patient's rights. An end of trial form must be completed and final drug accountability done even when patients are not able to come for a trial visit.

Only patients who withdraw their consent will be considered as withdrawn from the trial.

For patients who permanently discontinue from trial treatment (i.e. there is no plan to resume trial treatment or to enter the Extension Trial) every effort must be made to ensure patients attend and complete all scheduled visit procedures to the extent possible. Patients should stay in the trial regardless of compliance with trial drug, assessments, or visit schedule.

The investigators should make a special effort to ensure that all patients complete the assessment of actual PS volume in Week 24 (primary endpoint).

Patients who permanently discontinue from trial treatment and the trial (without withdrawal of consent) should be asked to come to the site for an EOT visit during which all general, safety, and laboratory assessments should be performed as detailed in the schedule of assessments. During this visit, the Investigator should also discuss further treatment options for SBS with the patient. Note: if a patient is discontinued during a trial visit, efforts should be made to complete all trial-related assessments for the EOT Visit. If not participating in the Extension Trial, the patient should attend the FU/Final visit.

A patient must be discontinued from trial treatment if:

1. Any safety concerns or AEs that in the opinion of the Investigator might place the patient at unacceptable risk, including any deterioration of a patient's health state, especially in terms of the frequency and volume of total PS.
2. Any malignancy.
3. Increased liver values, defined as:
 - a. ALT or AST >3 times baseline value lasting more than 2 weeks*, or
 - b. ALT or AST >5 × ULN and total bilirubin >2 x ULN*, or
 - c. ALT or AST >5 × ULN and INR >1.5*, or
 - d. ALT or AST >5 × ULN with the appearance of fatigue, nausea, vomiting, right upper quadrant pain or tenderness, fever, rash, and/or eosinophilia (>5%) %)*.
4. Pregnancy or intention to become pregnant.
5. The patient requires treatment with prohibited medications (see [Section 8.6](#)).

Patients can be discontinued from trial treatment if:

1. A patient was randomized despite it was later identified as having violated any of the inclusion, exclusion, or randomization criteria. The Investigator must discuss with the Sponsor's Medical Monitor if it is safe for the patient continue the trial treatment.

If a patient prematurely discontinues trial treatment, the primary reason must be specified in the eCRF and the Investigator must undertake procedures similar to those for the relevant visits as soon as possible. The intent should be to follow the patient to the extent possible according to the planned visit schedule and assessments with the purpose of following the safety and efficacy of the patients. Reason for trial visits not having been performed must be documented.

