5.3 Estimand

Translating the trial objective into a precise description of the treatment effect to be estimated, leads to four components that together define the estimand of interest:

1. The population is defined as patients with SBS randomized into the trial and having received treatment
2. The endpoint is the reduction from baseline in actual weekly PS volume after 24 weeks
3. The effect of twice weekly and once weekly glepaglutide 10 mg, regardless of discontinuing treatment or not, is of interest
4. The summary measure is the difference in endpoint means between active (twice weekly and once weekly glepaglutide 10 mg) and placebo

Estimand: Difference between mean reduction from baseline in actual weekly PS volume at 24 weeks in the SBS population regardless of whether treatment is discontinued.

The estimand is constructed based on the treatment policy strategy (ICH E9 (R1) addendum).

It is required to collect data after treatment discontinuation to get a reliable estimate of this estimand.

6 Investigational Plan

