10.5.1 Follow-up Visit (Week 28/Day 197 ± 7 days)

Patients who are not entering the Extension Trial should return the eDiary. During Follow-up Visit, the following assessments will be performed:

- Complete PROs (SBS-I and EQ-5D-5L)
- Record any procedures and changes to concomitant medications
- Record body weight
- Record vital signs (heart rate, systolic and diastolic blood pressure, and body temperature)
- Record AEs
- Perform short physical examination (driven by SBS symptoms)
- Collect urine sample for urinalysis
- Obtain blood samples for:
 - hCG pregnancy test (for females of childbearing potential only)
 - Hematology
 - Biochemistry
 - Citrulline
 - PK
 - ADA
- Review eDiary information for:
 - PS use
 - 48-hour oral fluid intake
 - 48-hour urine volume
 - 48-hour bowel movements/stoma bag emptying
- Complete end-of-trial form in the eCRF

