3. ENDPOINTS

3.1. PRIMARY EFFICACY ENDPOINT

The primary efficacy endpoint is the change in actual weekly PS volume from baseline to Week 24.

Baseline actual weekly PS volume is defined as the actual PS volume derived from a valid 7-day period prior to Visit 1 (Day 1), i.e. during the stabilization phase. The actual weekly PS volume at Weeks 1, 2, 4, 8, 12, 16, 20, and 24 will be derived as the actual weekly PS volume received during the valid 7-day period prior to the visit. The source for the derivation will be the PS volumes recorded by the patients in the eDiary; for details on the derivation of actual weekly PS volume see Appendix A. Supportive analyses will be performed to explore the robustness of the primary analysis with regard to the algorithm for deriving the primary endpoint, see 3.1.4.

Following the treatment policy strategy, for patients who prematurely discontinue treatment but complete the trial providing eDiary information up-to Week 24, the actual weekly PS volume derived at Week 24 after treatment discontinuation will be included in the primary analysis of the primary efficacy endpoint. For patients who prematurely discontinue treatment and did not complete the trial, having an end of treatment visit (Visit 10) prior to Week 24 - 14 days (169-14 days), the derived actual weekly PS volume at the end of treatment visit will not be carried forward to represent Week 24. Instead 1) the value at Week 24 will be set to missing and imputed with the multiple imputation method described below for the primary analysis of the primary endpoint and 2) the derived actual weekly PS volume at the end of treatment visit will be re-allocated to a previous visit and used in the MMRM model. If, when re-allocating the end of treatment visit there is already a visit in the same time window, then the value of the scheduled visit will be used in the analysis, not the re-allocated end of treatment value.

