3.1.3. Impact of COVID-19

No sensitivity analyses are planned to assess the impact of COVID-19 on any of the confirmatory efficacy endpoints since actual PS volume is collected in a daily electronic diary which is not dependent upon attending clinical visits per the protocol Schedule of Assessments. Refer to Risk Assessment and Conclusion document dated 30-Nov-2020 entitled "Covid-19 pandemic contingency plan for glepaglutide phase 3 trials; ZP1848-17111 (EASE SBS 1) and ZP1848-17127 (EASE SBS 2).

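### Protocol 7.5 both rules out and provides for leaving the trial without withdrawing consent, so obtainable Week 24 PS data can be lost to imputation

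*Protocol*

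**What the plan says.** Protocol 7.5 sets two retention rules: "Only patients who withdraw their consent will be considered as withdrawn from the trial", and "Patients should stay in the trial regardless of compliance with trial drug, assessments, or visit schedule". It also asks investigators for particular effort to obtain the Week 24 PS volume in all patients. The same section then describes a group outside those rules: "Patients who permanently discontinue from trial treatment and the trial (without withdrawal of consent) should be asked to come to the site". The purpose is an EOT visit, and the follow-up/final visit comes after it if they do not enter the Extension Trial.

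The primary estimand is treatment policy. On data after stopping drug, Protocol 5.3 says: "It is required to collect data after treatment discontinuation to get a reliable estimate of this estimand". SAP 2.3 repeats this.

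SAP 3.1 splits patients who stop drug early into two groups. Those who complete the trial with diary data to Week 24 contribute their observed value. For those who do not complete it and whose EOT visit falls more than 14 days before Day 169, "the value at Week 24 will be set to missing and imputed with the multiple imputation method", which for the primary analysis is Copy Reference.

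The source of the primary variable is the home eDiary. SAP 3.1.3, writing about COVID-19, notes that "actual PS volume is collected in a daily electronic diary which is not dependent upon attending clinical visits". Appendix A nevertheless derives a weekly volume only for scheduled visits that the patient attended.

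On diary return, Protocol 10.5.1 says "Patients who are not entering the Extension Trial should return the eDiary". That visit is nominally Week 28/Day 197, and Table 1 footnote 19 ties return to the same visit.

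**The concern.** Under the first rule in 7.5, a patient who leaves without withdrawing consent cannot exist. A few sentences later that patient has a defined route out. Two sites could read the section differently and both could claim to follow it.

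The consequence falls on the primary endpoint. Once such a patient has left, the SAP replaces the Week 24 value with one drawn from the placebo model, although the patient still consents and records PS at home. The estimand asks what happened to PS volume whether or not drug was stopped. Each avoidable exit replaces a direct answer with an assumption about how quickly benefit fades. Change in PS volume at Week 12, the third key secondary endpoint, is exposed in the same way for exits before that visit. The main analyses of the binary key secondary endpoints are not, because SAP 3.2 already counts treatment discontinuation as non-response.

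**Working it through.** **1. Cut-off.** 169 − 14 = Day 155. The missing-and-impute rule in SAP 3.1 applies to non-completers whose EOT visit is earlier than this.

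**2. Two patients who stop drug at Week 8, neither withdrawing consent.**
- *Patient A stays.* Protocol 7.5 and 7.6 direct follow-up on the planned schedule. The Week 24 visit is attended, Appendix A derives a volume, and SAP 3.1 uses it as observed.
- *Patient B takes the exit in 7.5.* The EOT visit is soon after Week 8 (about Day 57), well before Day 155, so SAP 3.1 imputes Week 24. Even if B keeps the diary to Day 169, Appendix A yields no Week 24 value, because no Week 24 visit was attended. The diary's independence from visits therefore does not help under the current derivation.

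**3. When does B hand in the diary?** The documents do not say. Section 7.5 is silent on the diary. Section 10.5.1 and footnote 19 place return at Day 197, which is after Week 24. No text moves that visit forward for early leavers, and no text tells the site to keep B's diary running to Day 169.

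**4. Is B a completer?** Protocol 6.4 counts a patient who attends the follow-up/final visit and does not enter the Extension Trial as having completed. SAP 3.1 makes its imputation rule depend on not having completed. B can be classed either way.

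**5. The plan's own figures.** Planned arm size is 108/3 = 36. Assumed changes are −4.5, −4.3 and −2.3 L/week, so the differences from placebo are 2.2 (twice weekly) and 2.0 (once weekly). With SD 2.62:

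SE = 2.62 × √(2/36) = 0.62 L/week.

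Power for at least one regimen, with two-sided α = 0.025 each and correlation 0.5 from the shared placebo arm, is 95.8% by the normal approximation and 95.3% by a t simulation. The stated figure is 95%, so it reproduces.

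**6. Size per exit.** The documents give no exit rate, so the counts below are assumptions. Suppose that both the imputed value and the unseen true value of an active-arm leaver lie, on average, between no benefit and full benefit. Then the gap in the estimated difference is at most (exits/36) × effect, in either direction.

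| Exits in an active arm (assumed) | Share of 36 | Bound, twice weekly (× 2.2) | Bound, once weekly (× 2.0) |
|---|---|---|---|
| 1 | 2.8% | 0.06 L/week | 0.06 L/week |
| 2 | 5.6% | 0.12 L/week | 0.11 L/week |
| 4 | 11.1% | 0.24 L/week | 0.22 L/week |

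Four exits would at worst shift the twice-weekly estimate by 0.24/0.62, about 0.4 of a standard error. No loss of power is claimed: Protocol 12.7 says the assumed means already include imputed effects.

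**The case against.** The strongest reply is that 7.5 is mainly a retention section and its odd sentence is a safety fallback. It asks patients who have stopped participating anyway to come in for safety and laboratory assessments; it does not tell sites to release anyone. Retention is stressed repeatedly in 7.5 and 7.6. Many patients who stop drug also have a reason to stay, because they may be invited to the Extension Trial only on finishing the 24-week schedule. Protocol 12.6 expects few discontinuations on active treatment. Jump to Reference, Copy Increments from Reference, tipping-point and observed-data analyses are all planned.

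Much of this stands, and it limits the point to a small subset. It does not remove the contradiction. The sensitivity analyses test the imputed values but do not recover data that a consenting patient could have supplied.

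Three stronger readings are tempting and should not be drawn:
- *That the protocol has early leavers hand in the diary about four weeks after stopping drug.* The return instruction belongs to the Day 197 visit. The contact roughly four weeks after stopping drug (Protocol 6.1 and Table 1 footnote 11) is for antibody sampling. Early return is possible under the wording but is not stated.
- *That Week 24 data after stopping drug are generally not collected.* They are collected and used for everyone who stays.
- *That the loss will differ by arm through adverse events.* Protocol 7.6 tells patients stopped for drug-related events to keep to the visit schedule as far as possible, and nothing in the documents shows a difference by arm or site.

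It is also fair to object that a diary alone may not be enough. Where diary days are missing, Appendix A compares the accounted volume with the investigator's prescription record, so a patient with no site contact would lack that input. The remedy has to cover this.

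**Conclusion.** The point holds in a limited form. Protocol 7.5 contradicts itself on whether a patient can leave the trial without withdrawing consent. For those who do so with an EOT visit before Day 155, SAP 3.1 and Appendix A together mean that Week 24 is imputed even when diary data could be had. That conflicts with the plan's own statement that such data are required.

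The size cannot be established from the documents. Each leaver is 2.8% of a 36-patient arm, with a bound of about 0.06 L/week on either treatment difference under the assumption in the working. The plan's expectation of few active-arm discontinuations suggests a small total. The case for changing the text rests on the low cost of recovering primary-endpoint data, not on a demonstrated threat to the trial's conclusion.

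**What to change.** - **Protocol 7.5:** remove the exit without consent withdrawal, or redefine it as no longer attending the site while remaining in the trial.
- **Protocol 10.5.1 and Table 1 footnote 19:** state that any patient who has not withdrawn consent keeps the eDiary and continues PS entries through Day 169, and that the diary is collected only after that. Add one telephone contact at Week 24 that also records the current PS prescription, so that the prescription check in Appendix A can be run.
- **SAP 3.1 and Appendix A:** count a valid diary window before nominal Day 169, or before the telephone contact, as the observed Week 24 value even when no site visit was attended. Without the Appendix A change, the extra diary data would still produce no value.
- **Protocol 6.4 and SAP 3.1:** use one definition of trial completion, so that an early leaver who attends the follow-up/final visit is classed the same way in both.

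The cost is protocol and SAP wording, slightly later diary collection and one call per affected patient. Some patients will decline to keep the diary, and the current imputation then applies to them. No dose, treatment-stopping rule or PS-adjustment rule changes.
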